3.13 REASONS FOR STUDY EXIT

Reasons for study exit are:

- Subject's withdrawal of consent from study
- Decision by sponsor to terminate the study
- Subject lost to follow-up
- Death

3.14 DATA AND SAFETY MONITORING

This trial will be monitored in accordance with the sponsor's pharmacovigilance procedures. Adverse events and SAEs will be reviewed internally on an ongoing basis to identify safety concerns. Quarterly conference calls with the investigators and applicable site staff will be conducted to discuss study progress, obtain investigator feedback and exchange, and discuss "significant safety events" (ie, AEs leading to dose reductions, related SAEs, and deaths). In addition, for the interim safety analysis, a mandatory safety teleconference will occur before the expansion phase of the protocol can open.

4.0 STUDY ACTIVITIES AND ASSESSMENTS

The schedule of events is provided in [Appendix 4](#) and [Appendix 5](#). Descriptions of the scheduled evaluations are outlined below and complete information on study drug and dosing is provided in [Section 3.4](#).

Before study entry, throughout the study, and at the follow-up evaluation, various clinical and diagnostic laboratory evaluations are outlined. The purpose of obtaining these detailed measurements is to ensure adequate safety and tolerability assessments. Clinical evaluations and laboratory studies may be repeated more frequently if clinically indicated. This study will primarily use central laboratory testing for safety laboratory evaluations. Samples from sites' local laboratories will be used if central laboratory testing is unavailable.

4.1 DESCRIPTION OF PROCEDURES

4.1.1 Informed Consent

The subject must read, understand and sign the ICF approved by the institutional review board or independent ethics committee (IRB/IEC), confirming his or her willingness to participate in this study before initiating any screening activity that is not considered standard of care by institutional standards. Subjects must also grant permission to use protected health information if required by local regulations.

4.1.2 Medical History

Collect and record the subject's complete history through review of medical records and by interview. Concurrent medical signs and symptoms must be documented to establish baseline severities. A disease history, including the date of initial diagnosis and list of all prior anticancer treatments, and responses and duration of response to these treatments, also will be recorded.

4.1.3 Adverse Events

The accepted regulatory definition for an AE is provided in [Section 6.1](#). All medical occurrences from the time of first dose that meet this definition must be recorded. Important additional requirements for reporting SAEs are explained in [Section 6.2](#).

4.1.4 Concomitant Medications and Therapy

Document all concomitant medications and procedures from within 28 days before the start of study drug administration through 30 days after the last dose of study drug.

4.1.5 Confirmation of Eligibility

Subject eligibility for enrollment will be assessed per [Section 3.3](#). All screening procedures, unless otherwise indicated, should be completed within 28 days of the first dose of study drug.

4.1.6 ECOG Performance Status

The ECOG performance index is provided in [Appendix 1](#).

4.1.7 Physical Examination, Vital Signs, Height & Weight

The screening physical examination will include, at a minimum, the general appearance of the subject, height (screening only) and weight, and examination of the skin, eyes, ears, nose, throat, lungs, heart, abdomen, extremities, musculoskeletal system, nervous system, and lymphatic system.

Symptom-directed physical exams will be done during the treatment period and at the safety follow-up visits.

Vital signs (blood pressure, heart rate, respiratory rate, and body temperature) will be assessed after the subject has rested in the sitting position.

4.1.8 Electrocardiogram

Subjects should be in supine position and resting for at least 10 minutes before any study related ECGs. Before first dose of study drug on Day 1, Week 1, 3 ECGs will be done at least 1 minute apart. These ECGs and the screening ECG will be considered the baseline ECGs. If an unscheduled ECG is done at any time, then an electrolyte panel (ie, calcium, magnesium, and potassium) must be done to coincide with the ECG testing.

Single on-treatment ECGs will be done at any time during the following visits:

- Week 2
- Week 4
- Week 7
- Early termination and/or safety follow-up visit

4.1.9 Urine or Serum Pregnancy Test

Pregnancy tests will be required only for women of childbearing potential. Women of childbearing potential must have a negative urine or serum pregnancy testing within 72

hours prior to receiving the first dose of study medication. If the urine test is positive or cannot be confirmed as negative, a serum pregnancy test is required. Testing will be done by a local or central laboratory as listed on the investigator's Form FDA 1572.

4.1.10 Hematology

Hematology studies must include complete blood count (CBC) with differential and platelet and reticulocyte counts. Testing will be done by a local or central laboratory as listed on the investigator's Form FDA 1572.

4.1.11 Serum Chemistry

Chemistry will include albumin, alkaline phosphatase, ALT, AST, bicarbonate, blood urea nitrogen (BUN), bone-specific alkaline phosphatase, calcium, chloride, creatinine, glucose, lactate dehydrogenase (LDH), magnesium, phosphate, potassium, sodium, total bilirubin, total protein, and uric acid. If an unscheduled ECG is done at any time, then an electrolyte panel (ie, calcium, magnesium, and potassium) must be done to coincide with the ECG testing. Testing will be done by a local or central laboratory as listed on the investigator's Form FDA 1572.

4.1.12 Amylase and Lipase

Serum amylase and serum lipase testing will be performed at the study center's local laboratory or other clinical laboratory listed on the investigator's form FDA 1572.

4.1.13 Thyroid Panel

The thyroid panel will include total triiodothyronine (T3), free thyroxine (T4), and thyroid stimulating hormone (TSH). Testing will be done by a local or central laboratory as listed on the investigator's Form FDA 1572.

4.1.14 Hepatitis B and C Testing

Hepatitis serology testing must include hepatitis B surface antigen (HBsAg), hepatitis B surface antibody (anti-HBs), hepatitis B core antibody (anti-HBc), and hepatitis C (HCV) antibody. In addition, any subjects testing positive for any hepatitis serology, must have PCR testing performed during screening and on study (see [Appendix 4](#) and [exclusion criterion #27](#)). Testing will be done by a local or central laboratory.

Subjects who are anti-HBc positive should have quantitative PCR testing for HBV DNA performed during screening and monthly thereafter. Monitoring should continue every 4 weeks (\pm 7 days) until 12 months after last dose of study drug(s). Any subject with a

rising viral load (above lower limit of detection) should discontinue study drug and have antiviral therapy instituted and a consultation with a physician with expertise in managing hepatitis B.

Subjects with a known history of hepatitis C or who are hepatitis C antibody positive should have quantitative PCR testing for HCV DNA performed during screening and at Weeks 13 and 25. No further testing beyond Week 25 is necessary if PCR results are negative.

Refer to [Section 3.10.2](#) and [Appendix 4](#) regarding monitoring of subjects who are anti-HBc positive or hepatitis C antibody or who have a known history of HBV or hepatitis C.

4.1.15 Urinalysis

Urinalysis includes pH, ketones, specific gravity, bilirubin, protein, blood, and glucose. Testing will be done by a local or central laboratory as listed on the investigator's Form FDA 1572.

4.1.16 T/B/NK Cell Count

Flow cytometry testing will include CD3⁺, CD4⁺, CD8⁺, CD19⁺, and CD16/56⁺ cells. Testing will be done by a local or central laboratory as listed on the investigator's Form FDA 1572.

4.1.17 Serum Immunoglobulin

Testing for IgG, IgM, and IgA will be done by a local or central laboratory as listed on the investigator's Form FDA 1572.

4.1.18 Pharmacodynamics/Pharmacokinetics and Biomarker Studies

Blood samples will be used for PD testing including, but not limited to, BTK occupancy, B-cell activation, MDSCs, and T-cell activation, cytokine analysis, and for further characterization of circulating tumor cells, lymphocyte and myeloid cell subsets.

Tissue sections from archival tumor biopsies and/or any newly obtained biopsies performed during the study will be used for exploratory biomarker studies (including, but not limited to, expression of PD-L1, characterization of disease subtype, and evaluations of MDSCs and activated CD8⁺ cells). Additional exploratory studies may include, but are not necessarily limited to, characterization of BTK pathway activation status, identification disease subtype, specific genetic markers with prognostic significance and

evaluation of tumor microenvironment components and cell cycle proteins in malignant cells. If available, de-identified pathology reports from the most recent diagnostic work-up, including immunohistochemistry and cytogenetic analyses of tumor tissue, may be requested by the sponsor.

Refer to the laboratory manual for instructions on collection and shipment of the PD and biomarker samples. All testing will be done by the sponsor or designee. Leftover blood and tumor samples may also be used for genomic analyses to study mechanisms of action.

Blood sampling for PK analysis of acalabrutinib will be done on all subjects in the combination arm only and intensive PK will be on the first 6 subjects enrolled in the combination arm. For these first 6 subjects, acalabrutinib will be administered alone on Day 1/Week 1. Then on Day 2/Week 1 the first pembrolizumab infusion will be administered. When PK sampling is done at Week 3 and Week 7, the pembrolizumab infusion should begin within 10 minutes of ingesting acalabrutinib. The PK sampling timepoints for these 6 subjects is as follows:

Visit	PK Sample Timepoints Relative to Acalabrutinib Administration
Day 1, Week 1	predose and 0.5, 1, 2, and 4 hours
Day 2, Week 1	predose
Week 3	predose and 0.5, 1, 2, and 4 hours postdose
Week 7	predose and 0.5, 1, 2, and 4 hours postdose

For all other subjects enrolled in the combination arm, PK sampling will be done predose and 1 hour postdose on Week 3.

The predose sample can be taken up to 30 minutes before dosing. The window for all other timepoints is \pm 5 minutes. Leftover plasma from PK analysis may be repurposed for exploratory acalabrutinib plasma metabolite analysis. Testing will be done by a central lab. Refer to the laboratory manual for instructions on collection and shipment of PK samples.

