2.3 EXPLORATORY OBJECTIVES

- Determine the effects of acalabrutinib plus pembrolizumab on peripheral blood T cells and MDSCs
- Determine the PK of acalabrutinib alone and in combination with pembrolizumab
- Determine if any characteristics of peripheral blood T cells and/or MDSCs correlate with immune-mediated toxicities
- Determine if any characteristics of peripheral blood T cells and/or MDSCs correlate with response to acalabrutinib and pembrolizumab
- Determine if any baseline tumor characteristics correlate with response to acalabrutinib and pembrolizumab
- Evaluate the efficacy of adding acalabrutinib to pembrolizumab in subjects who progress on pembrolizumab monotherapy

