3.1.2 Pharmacodynamic, Pharmacokinetic and Biomarker Parameters

The occupancy of BTK by acalabrutinib will be measured in PBMCs with the aid of a biotin-tagged acalabrutinib analogue probe. The effect of acalabrutinib and pembrolizumab on B cells, T cells and MDSCs will also be evaluated. Tumor tissue, when available, will be evaluated for PD-L1 expression. Additional exploratory correlative studies of tumor tissue, when available, may include characterization of tumor subtypes by immunohistochemistry, gene expression or mutation analysis.

The following PK parameters will be calculated, whenever possible, from plasma concentrations of acalabrutinib:

- $AUC_{0\text{-last}}$: Area under the plasma concentration-time curve calculated using linear trapezoidal summation from time 0 to time last, where “last” is the time of the last measurable concentration.
- $AUC_{0\text{-}12}$: Area under the plasma concentration-time curve from 0 to 12 hours, calculated using linear trapezoidal summation.
- $AUC_{0\text{-}inf}$: Area under the plasma concentration-time curve from 0 to infinity, calculated using the formula: $AUC_{0\text{-}inf} = AUC_{0\text{-}last} + C_{last} / \lambda_z$, where λ_z is the apparent terminal elimination rate constant.
- $AUC_{0\text{-}24\text{calc}}$: Area under the plasma concentration-time curve from 0 to 24 hours, calculated by doubling the value for $AUC_{0\text{-}12}$
- C_{max} : Maximum observed plasma concentration
- T_{max} : Time of the maximum plasma concentration (obtained without interpolation)
- $t_{1/2}$: Terminal elimination half-life (whenever possible)
- λ_z : Terminal elimination rate constant (whenever possible)
- CL/F : Oral clearance
- Vz/F : Oral volume of distribution

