3.5.2 Arm 2 – Combination Treatment

The dose of acalabrutinib is 100 mg BID PO. The doses may be modified for DLTs as summarized in [Table 3-2](#).

Pembrolizumab 200 mg will be administered every 3 weeks by IV infusion for a maximum of 24 months from the date of first dose.

Acalabrutinib and pembrolizumab dosing will begin on the same day (Day 1 of Week 1) except for the first 6 subjects enrolled due to PK sampling. The first 6 subjects enrolled will receive acalabrutinib on Day 1 of Week 1. Then on Day 2 of Week 1 the first pembrolizumab infusion will be administered.

Table 3-2. Dose Reduction for Acalabrutinib

Dose Level	Acalabrutinib	Pembrolizumab
Starting Dose	100 mg BID PO	200 mg Q3W IV
Level -1	100 mg QD PO	200 mg Q3W IV
Level -2	50 mg BID PO	200 mg Q3W IV

Abbreviations: BID = twice per day; IV = intravenous, PO = oral; Q3W = every 3 weeks; QD = once per day

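### The PK section ties a pembrolizumab infusion to the Week 3 visit, which every-3-week dosing does not make an infusion visit; and AUC0-12 and AUC0-24calc cannot be computed as defined from samples that end at 4 hours

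*Protocol*

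**What the plan says.** **Infusion schedule.** Section 3.5.2 states for Arm 2: "Pembrolizumab 200 mg will be administered every 3 weeks by IV infusion for a maximum of 24 months from the date of first dose". Dosing starts on Day 1 of Week 1, except that for the first six subjects "Then on Day 2 of Week 1 the first pembrolizumab infusion will be administered". Sections 3.4.4 and 3.8 keep missed or held infusions on the original 3-week schedule.

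**PK visits.** Section 4.1.18 gives the first six Arm 2 subjects intensive sampling in Week 1 (Days 1 and 2), Week 3 and Week 7. The last sample of each profile is at 4 hours. For the rest: "For all other subjects enrolled in the combination arm, PK sampling will be done predose and 1 hour postdose on Week 3". Footnote r of Appendix 4 agrees.

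**Co-administration rule.** Section 4.1.18: "When PK sampling is done at Week 3 and Week 7, the pembrolizumab infusion should begin within 10 minutes of ingesting acalabrutinib". Section 3.4.3 gives the 10-minute rule for PK sampling in general, without naming a week or a group of subjects.

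**Purpose and parameters.** The exploratory objective in Section 2.3 is: "Determine the PK of acalabrutinib alone and in combination with pembrolizumab". Section 3.1.2 defines AUC0-12 as: "Area under the plasma concentration-time curve from 0 to 12 hours, calculated using linear trapezoidal summation". It then obtains AUC0-24calc by doubling AUC0-12.

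**The concern.** Two instructions to sites do not fit together. One fixes infusions 3 weeks apart from Week 1. The other presupposes an infusion at a visit two weeks after the first dose. A site has to decide for itself what the Week 3 instruction means. If sites decide differently, the Week 3 samples are taken under mixed conditions, and the data will not show which condition was intended. For most of Arm 2 this is the only PK visit, so no later visit compensates.

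The second mismatch is between parameters and samples. A trapezoid to 12 hours needs an observation at or near 12 hours, and the profiles stop at 4. Doubling AUC0-12 then carries whatever was done about the missing 8 hours into the daily exposure figure.

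**Working it through.** **Arm size.** The plan allows up to 37 per arm. An unpooled Z-test with 40% against 18%, one-sided alpha 0.10 and 80% power gives (1.2816 + 0.8416)² × (0.40×0.60 + 0.18×0.82) / 0.22² = 4.508 × 0.3876 / 0.0484 = 36.1, so 37. The pooled form gives 38, and power at 37 is 79.6%. The figure of 37 stands and is used below as a denominator.

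**Infusion weeks.** Infusion day = first day + 21k; week = floor((day − 1)/7) + 1.

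| First infusion | Infusion days | Weeks |
|---|---|---|
| Day 1 | 1, 22, 43, 64, 85 | 1, 4, 7, 10, 13 |
| Day 2 (first six) | 2, 23, 44, 65, 86 | 1, 4, 7, 10, 13 |

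The worked example in Appendix 5 (crossover at Week 10, back to the main schedule at Week 13) fits this grid. The dosing rows of Appendix 4 cannot be read column by column in the text version, so nothing here rests on them.

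**Does the visit window close the gap?** With ± 3 days, the Week 3 visit spans Days 12-18. The second infusion spans Days 19-25, or 20-26 from a Day 2 start. They do not overlap. Week 7 (Day 43) does fall on the grid.

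**Subjects affected.** Sampled only at Week 3: 37 − 6 = 31 of 37 (84%) at full enrolment. Sampled on an infusion day with both drugs given: the first six, at Week 7.

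**Is pembrolizumab present at Week 3?** The package insert (Appendix 6, Section 12.3) gives a terminal half-life of 27 days. By a simple single-exponential approximation, the fraction of the first dose left 14 days later is 2^(−14/27) = 0.70.

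**Share of AUC0-12 after 4 hours.** Assumption: one-compartment oral model, single dose, with C(t) proportional to exp(−ke·t) − exp(−ka·t). Here ke = ln 2 / half-life, and ka solves ln(ka/ke)/(ka − ke) = Tmax. The area to time t is A(t) = (1 − e^(−ke·t))/ke − (1 − e^(−ka·t))/ka, and the share is 1 − A(4)/A(12). Half-lives of 0.97-2.1 h and Tmax of 0.5-1.0 h come from Part 1 of the healthy-volunteer study in Section 1.7.1. The 3.3 h half-life is from Part 3 of that study. The 1.5 h row is an intermediate value.

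| Half-life | Share, Tmax 0.5 h | Share, Tmax 1.0 h |
|---|---|---|
| 0.97 h | 6.9% | 11.6% |
| 1.5 h | 16.9% | 20.6% |
| 2.1 h | 26.7% | 29.7% |
| 3.3 h | 39.4% | 41.6% |

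Example (2.1 h, Tmax 0.5 h): ke = 0.330, ka = 6.19, A(4) = 2.059, A(12) = 2.811, share = 1 − 2.059/2.811 = 26.7%.

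**Could the predose sample stand in for the 12-hour value?** In the same example C(4) = 0.267 and C(12) = 0.019. One linear trapezoid from 4 to 12 h gives 4 × (0.267 + 0.019) = 1.14, against a true area of 2.811 − 2.059 = 0.75. The excess of 0.39 is 14% of AUC0-12. Over the grid above the excess is about 9-21%.

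**The case against.** **The objective does not ask for infusion-day samples.** This stands. It asks for acalabrutinib PK alone and in combination. With roughly 70% of the first pembrolizumab dose remaining at Day 15, every Week 3 sample is taken with pembrolizumab on board. In the first six subjects, Day 1 (acalabrutinib alone) can be compared with Weeks 3 and 7. A reader might infer that most of Arm 2 has no combination PK at all; the documents do not support that. What those subjects lack is same-day co-administration PK, which is the condition the 10-minute rule was written to standardise.

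**The 10-minute rule may apply only when both drugs are due.** In Section 3.4.3 it follows a sentence about same-day administration, so a site could treat it as having no effect at a visit without an infusion. That is a fair reading of Section 3.4.3. It does not dispose of Section 4.1.18, which names Week 3. That sentence sits in text about the first six subjects, so its reach to the others rests on the general wording of Section 3.4.3. A reader might also infer that Arm 2 would be infused off schedule and diverge from Arm 1. That is only one possible site response, and the protocol repeatedly states the 3-week interval.

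**The PK parameters are already qualified.** Section 3.1.2 says they are calculated where possible, lists AUC0-last, and extrapolates from the terminal slope for AUC0-inf. This softens the AUC point. It does not make the AUC0-12 definition match the samples, because no extrapolation is given for AUC0-12 and none of the profiles supports it as written.

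**Everything affected is exploratory.** True. No primary or secondary endpoint, sample size or stopping rule is touched.

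**Conclusion.** The contradiction holds and needs no modelling: Week 3 is not an infusion visit on the stated schedule, the visit window does not make it one, and Section 4.1.18 instructs as if it were. It bears on the only PK visit of up to 31 of 37 Arm 2 subjects at full enrolment. Same-day co-administration PK then comes from six subjects at Week 7. The exploratory objective is weakened rather than lost.

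The AUC mismatch also holds. With no sample after 4 hours, AUC0-12 by linear trapezoid and its doubled value cannot be obtained as defined. The unobserved share, about 7-30% at half-lives of 0.97-2.1 h and 39-42% at 3.3 h, depends on the one-compartment assumption and on healthy-volunteer values. It indicates size and does not predict what this population will show. The AUC point concerns the first six subjects, since two samples per subject give the rest no profile.

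**What to change.** Reconcile Sections 3.4.3, 3.5.2 and 4.1.18 with the PK row and footnote r of Appendix 4, so that the PK visits and the co-administration instruction agree with the infusion schedule. Which passage gives way is for the sponsor to decide. State also whether the 10-minute rule covers all Arm 2 subjects or only the first six.

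For the PK analysis, do one of two things:

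- Report AUC0-4 (AUC0-last) in place of trapezoidal AUC0-12, and drop AUC0-24calc.
- Define AUC0-12 with extrapolation from the terminal slope, and label it as extrapolated.

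The cost is a few lines of wording. The first option gives a less complete exposure measure. The second rests on the 1, 2 and 4 hour samples at most for the slope. Neither needs extra samples.

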In Part 2, the effect of food on the PK of acalabrutinib (75 mg) after a single oral administration was evaluated in 6 men and 6 women. Median time to maximum plasma acalabrutinib (T_{max}) values were increased in the fed state (2.5 hours) relative to the fasted state (0.5 hour). The mean plasma acalabrutinib C_{max} fed values decreased to 27.3% of the C_{max} values observed in the fasted state. In contrast, the relative AUC exposure of acalabrutinib remained mostly unchanged in both states. This decrease in exposure is not clinically significant; therefore, acalabrutinib can be taken without regard to meals.

In Part 3, the effect of itraconazole on the PK of acalabrutinib (50 mg) after a single oral administration was evaluated in 17 subjects. No difference in acalabrutinib T_{max} values was observed in the presence or absence of itraconazole.

Mean acalabrutinib exposures (as assessed by C_{max} , AUC_{0-last} , AUC_{0-24} , and AUC_{0-inf}) increased in the presence of itraconazole. The mean plasma acalabrutinib C_{max} values increased 3.7-fold in the presence of itraconazole. The mean plasma AUC_{0-last} , AUC_{0-24} , and AUC_{0-inf} values also increased between 4.9- to 5.1-fold in the presence of

itraconazole. Mean CL/F and Vz/F values decreased in the presence of itraconazole (CL/F: 217 vs 44 L/h; Vz/F: 1190 vs 184 L). No differences in half-life values were observed (3.3 vs 2.5 hours).

The PD of acalabrutinib was evaluated using a BTK occupancy assay and correlated with a functional assay that determines the level of BTK inhibition by measuring expression of CD69 and CD86 on B cells. A dose-dependent increase in BTK occupancy and corresponding decrease in CD69/86 expression was observed in this study. Full BTK occupancy ($\geq 90\%$) and complete CD86 and CD69 inhibition ($\geq 90\%$) occurred at the 75- and 100-mg single dosed cohorts 1 to 3 hours after administration. However, only the 100-mg cohort maintained high BTK occupancy (91.5%) and high BCR functional inhibition (CD86: $86 \pm 3\%$ and CD69: $78 \pm 8\%$) at 24 hours. For subjects receiving a second dose of acalabrutinib 12 hours after the first administration, full BTK target occupancy was observed 3 hours after the second dose for the 50-mg dosed cohort (BTK occupancy $97 \pm 4\%$).

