3.10.3 Dietary Restrictions

Acalabrutinib can be taken with or without food. Because acalabrutinib is metabolized by CYP3A, subjects should be strongly cautioned against excessive consumption of grapefruit, grapefruit juice, or Seville orange juice (which contain potent CYP3A inhibitors) or using herbal remedies or dietary supplements (in particular, St John's wort, which is a potent CYP3A inducer).

Otherwise subjects should maintain a normal diet unless modifications are required to manage an AE such as diarrhea, nausea or vomiting.

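### Fed or fasted state is neither held constant nor recorded on acalabrutinib PK days, so the exploratory alone-versus-combination comparison of Cmax, Tmax and 1 h values is open to food confounding

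*Protocol*

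**What the plan says.** One exploratory objective in Section 2.3 reads "Determine the PK of acalabrutinib alone and in combination with pembrolizumab". Section 4.1.18 serves it in two ways.

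- "intensive PK will be on the first 6 subjects enrolled in the combination arm". These subjects take acalabrutinib alone on Day 1 of Week 1, with samples before the dose and at 0.5, 1, 2 and 4 h. The same profile is repeated at Week 3 and Week 7.
- "For all other subjects enrolled in the combination arm, PK sampling will be done predose and 1 hour postdose on Week 3".

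Section 4.1.18 allows ±5 minutes for each postdose sample. It refers collection and shipment of samples to the laboratory manual.

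On food, Section 3.10.3 says "Acalabrutinib can be taken with or without food", with no exception for PK days. The dosing instructions (Section 3.4.3) mention water and certain juices but not meals. The diary in Section 3.4.4 captures dose times and reasons for missed doses. The PK footnote to Appendix 4 lists visits only.

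The food-effect part of ACE-HV-001, summarised in Section 1.7.1, gave single 75 mg doses to 12 volunteers. Mean Cmax "fed values decreased to 27.3% of the" fasted values, and median Tmax was 2.5 h fed against 0.5 h fasted. By contrast, "the relative AUC exposure of acalabrutinib remained mostly unchanged in both states". The section concludes that "acalabrutinib can be taken without regard to meals".

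**The concern.** The comparison of acalabrutinib alone with acalabrutinib plus pembrolizumab is made within subjects, between occasions, in six people. Any factor that differs between Day 1 and Week 3 or Week 7 enters it directly. The protocol controls sampling time to minutes but leaves free a factor that, on its own data, moves median Tmax by two hours and cuts mean Cmax by more than two thirds.

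A subject who fasts on Day 1 and eats before the Week 3 dose would show a fall in Cmax that looks like an interaction. The reverse sequence could hide one. If meals are not recorded, no later analysis can separate the two explanations.

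The other Arm 2 subjects (up to 31) have no acalabrutinib-alone occasion, so they do not contribute to that comparison. Their single postdose sample has its own difficulty: 1 h lies after the median fasted peak and before the median fed peak, so the value is hard to interpret without the prandial state.

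**Working it through.** **Inputs from Section 1.7.1.** Fed/fasted Cmax ratio 0.273; median Tmax 0.5 h fasted and 2.5 h fed; mean half-life 0.97 to 2.1 h (Part 1 of the same study). **From Section 4.1.18.** Six intensive-PK subjects; last postdose sample at 4 h.

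**Fold change.** 1/0.273 = 3.66, a derived figure. The 3.7-fold change in Cmax printed in Section 1.7.1 is the itraconazole effect and should not be cited for food.

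**Effect on the six-subject ratio.** Assume no true interaction, and that the 75 mg healthy-volunteer food effect applies to every subject at the trial dose. Let k be the number of subjects going from fasted to fed minus the number going from fed to fasted, between Day 1 and a later visit. The geometric mean Cmax ratio due to food alone is 0.273^(k/6).

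| Net k | Net change fasted to fed | Net change fed to fasted |
|---|---|---|
| 0 | 1.00 | 1.00 |
| 1 | 0.81 | 1.24 |
| 2 | 0.65 | 1.54 |
| 3 | 0.52 | 1.91 |

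One switch in each direction returns the ratio to 1.00.

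**How much chance alone could produce.** The protocol says nothing about how often subjects eat before PK doses, so this step is assumption only. Suppose each occasion is fed independently with probability q. The standard deviation of the log ratio is |ln 0.273| × √(2q(1−q)/6), with |ln 0.273| = 1.298.

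- q = 0.5: 1.298 × √(0.5/6) = 0.375, so the approximate 95% range is exp(±1.96 × 0.375) = 0.48 to 2.08.
- q = 0.25 or 0.75: 1.298 × √(0.375/6) = 0.325, so the range is 0.53 to 1.89.

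Taking 0.80 to 1.25 as a yardstick (the protocol sets no bound), a net switch of two or more is needed to leave it. The exact multinomial probability is 39% at q = 0.5 and 31% at q = 0.25 or 0.75. Subjects with steady breakfast habits would vary less.

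**The 1 h value and AUC to 4 h.** These need a model. An illustrative one-compartment oral model with equal total AUC, Tmax of 0.5 or 2.5 h and half-life 0.97 to 2.1 h gives:

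- 1 h concentration, fed/fasted: 0.22 to 0.42;
- trapezoidal AUC0-4 on the protocol's sampling times, fed/fasted: 0.41 to 0.65;
- the model's own Cmax ratio: 0.24 to 0.52. The reported 0.273 lies near the short half-life end, so the model is only a rough guide.

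**The case against.** The strongest reply is that the same paragraph of Section 1.7.1 reports AUC mostly unchanged and judges the food effect not clinically significant. This stands as far as total exposure goes, and it supports the treatment-day instruction. A reader might infer from the Cmax figure that food disturbs total acalabrutinib exposure; the documents do not support that. The protection is incomplete here, though, because postdose sampling stops at 4 h. With a fed Tmax of 2.5 h only the 4 h sample follows the peak, which makes the terminal slope, and the AUC0-inf in Section 3.1.2 that depends on it, hard to estimate. The size of any AUC0-4 distortion comes from an assumed model, hence only possibly.

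Second, the objective is exploratory, with no test, bound or decision rule. That is correct and limits the weight of the point. Yet the first pembrolizumab infusion is moved to Day 2 in these six subjects because of PK sampling, so the data are meant to be interpretable.

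Third, the laboratory manual and PK form are not at hand and might cover meals. The protocol refers only collection and shipment to the manual, so the statement here is confined to the protocol.

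Fourth, sampling under the permitted food rule describes exposure as the drug is used. That is reasonable for description, but not for a between-occasion comparison in six people.

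A reader might also infer that the gap undermines an exposure explanation of the transaminase elevations. The protocol states no such analysis: Section 2.3 relates immune-mediated toxicity to T cells and MDSCs, and Section 5.4.5 mentions further PK analyses and correlations only in general terms.

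**Conclusion.** The point holds, with limited scope. Followed as written, the protocol leaves the exploratory alone-versus-combination comparison open to food confounding for Cmax, Tmax and the 1 h concentration, and possibly for AUC observed to 4 h. It also leaves the single 1 h postdose value in the other Arm 2 subjects hard to interpret. Primary and secondary endpoints are not touched.

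The ratios of 0.81, 0.65 and 0.52 are illustrations, not predictions. They carry a mean effect from 75 mg single doses in healthy volunteers over to 100 mg BID in patients, give every subject that same effect, and require a net switch in one direction. One net switch is a modest bias; two or more would be hard to tell from an interaction. The documents give no switching frequency and no between-occasion variability to set against these figures.

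Standardising meals will not settle everything about the Week 3 sample. Section 4.1.18 has pembrolizumab infused within 10 minutes of acalabrutinib at Week 3, whereas dosing every 3 weeks from Week 1 (Section 3.5.2) falls on Weeks 4 and 7. Those passages must be reconciled separately.

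**What to change.** Add to Section 4.1.18 that each intensive-PK subject takes the observed acalabrutinib dose in the same prandial state on Day 1 of Week 1, at Week 3 and at Week 7, with the state chosen by the sponsor. Record last-meal time and dose time for every PK occasion in all Arm 2 subjects.

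Summarise Cmax, Tmax and 1 h values by recorded state. Flag occasions on which a subject's state differs from the other visits and show them in a sensitivity summary; automatic exclusion would cost too much with six subjects. The with-or-without-food instruction in Section 3.10.3 stays unchanged.

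The cost is a minor meal-timing constraint for six subjects on three visits and two fields on the PK form. No extra samples or visits are needed. With the state held constant within each subject, food contributes a Cmax ratio of 1.00 to the comparison under the same assumptions.
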